## 7.4 Analysis Periods

Analysis periods are defined as follows:

- eDiary efficacy endpoints (migraine days, rescue medication days), based on the date part of derived date/times
  - OP: Reference time point date in the OP epoch (see Section 7.6.2.1).
  - On-DBT efficacy: Reference time point date in the DBT epoch on or before the DBT last date + 1 day. This period is used to assess efficacy during the DBT phase.
  - Post-DBT pre-OL rimegepant efficacy: Reference time point date in the DBT epoch after the DBT last date + 1 day. This period is used only in eDiary efficacy listings.
  - On-OL rimegepant efficacy: Reference time point date in the OLE epoch on or before the OL rimegepant last date + 1 day. This period is used to assess efficacy during the OLE phase.

- Follow-up efficacy: Reference time point date in the OLE epoch after the OL rimegepant last date + 1 day. This period is used only in eDiary efficacy listings.
  - OR efficacy endpoints (MSQoL, MIDAS)
    - On-DBT efficacy: Measurement date after the DBT start date through the earlier of (1) DBT last date + 1 day and (2) OL rimegepant start date. This period is used to assess OR efficacy during the DBT phase for evaluable mITT subjects.
  - Pre-treatment characteristics and safety endpoints
    - Pre-treatment: Measurement date/time on or before the study drug start date/time. Note that AEs with imputed start date equal to the study drug start date are **not** part of this period (refer to the BHV3000 Core SAP for AE start date imputation). This period is used to derive baseline values and to assess pre-treatment safety endpoints.
    - Pre-rimegepant: Measurement date/time on or before the DB or OL rimegepant start date/time. Note that AEs with imputed start date equal to the DB or OL rimegepant start date are **not** part of this period. This period is used to derive rimegepant baseline values and to assess pre-rimegepant safety endpoints for DB or OL rimegepant treated subjects.
    - On-DBT safety: Measurement date/time after the DBT start date/time through the earlier of DBT last date + 7 days and OL rimegepant start date/time. Note that AEs with imputed start date equal to the DBT start date are part of this period, while AEs with imputed start date equal to the OL rimegepant start date are **not** part of this period. This period is used to assess safety endpoints on DBT.
    - Post-DBT pre-OL rimegepant safety: Measurement date/time after the DBT last date + 7 days through the OL rimegepant start date/time. Note that AEs with imputed start date equal to the OL rimegepant start date are **not** part of this period. This period is used in safety listings to distinguish measurements, and to assess safety endpoints during the interim period (i.e., post-DBT pre-OL rimegepant) for interim subjects (i.e., those with > 7-day gap between DBT last date and OL rimegepant start date).
    - On-OL rimegepant safety: Measurement date/time after the OL rimegepant start date/time through the study drug last date + 7 days. Note that AEs with imputed start date equal to the OL rimegepant start date are part of this period. This period is used in safety listings to distinguish measurements, and to assess safety endpoints for OL rimegepant treated subjects in the blinded 90-Day Safety Update.
    - On-DB or OL rimegepant safety: Measurement date/time after the DB or OL rimegepant start date/time through the DB or OL rimegepant last date + 7 days. Note that AEs with imputed start date equal to the DB or OL rimegepant start date are part of this period. This period is used to assess safety endpoints on DB or OL rimegepant treatment for DB or OL rimegepant treated subjects.
    - On-treatment safety: Measurement date/time after the study drug start date/time through the study drug last date + 7 days. Note that AEs with imputed start date equal to the study drug start date are part of this period. This period is the on-DBT and on-OL rimegepant safety periods combined, and will be used to assess safety endpoints for treated subjects in the blinded 90-Day Safety Update.
-

- Follow-up safety: Measurement date after the study drug last date + 7 days. This period is used to assess safety endpoints during follow-up for follow-up subjects.
- Non-efficacy OR endpoints (see Section 6.6)
  - DBT OR: Measurement date after the DBT start date to the OL rimegepant start date. This period is used to assess OR during the DBT phase.
  - OL rimegepant OR: Measurement date after the OL rimegepant start date. This period is used to assess OR during the OLE phase.

See Section 7.3 for derived dates for determining analysis periods.

If measurement time is missing or not collected for a parameter, then the measurement date will be compared to the derived date.

## 7.5 Analysis Visit Windows

Refer to BHV3000-305 Protocol Section 4.3 (Tables 1 and 2) for the schedule of assessments.

Randomization days are calculated from randomization as follows:

- Measurement date – IWRS randomization date + 1, if measurement date  $\geq$  IWRS randomization date
- Measurement date – IWRS randomization date, if measurement date  $<$  IWRS randomization date.

Study days are calculated from study drug start as follows:

- Measurement date – study drug start date + 1, if measurement date  $\geq$  study drug start date
- Measurement date – study drug start date, if measurement date  $<$  study drug start date.

Rimegepant study days are calculated from DB or OL rimegepant start as follows:

- Measurement date – DB or OL rimegepant start date + 1, if measurement date  $\geq$  DB or OL rimegepant start date
- Measurement date – DB or OL rimegepant start date, if measurement date  $<$  DB or OL rimegepant start date.

Follow-up days are calculated from the study drug last as follows:

- Measurement date – study drug last date + 1, if measurement date/time  $\geq$  study drug last date
- Measurement date – study drug last date, if measurement date  $<$  study drug last date.

Analysis visit windows presented in Table 4 below are based on study days (see Section 7.4).

---

### Table 4: Analysis Visit Windows for Non-Efficacy Endpoints

Analysis Period Analysis Visit	Abbreviation in Listings	Analysis Day Analysis Visit Window	Target Day
Pre-Treatment	PRETRT	Randomization Day	
Screening		≤ -7 or missing	
Pre-Randomization	Prerand	-6 to -1	
Randomization	Rand	1	
Post-Randomization	Postrand	≥ 2	
OR/On-Treatment Safety *	OR: DBT or OLRMG Safety: DBT, INT, or OLRMG	Study Day	
Week 2		1 to 21	14
Week 4		22 to 42	28
Week 8		43 to 70	56
Week 12		71 to 91	84
Week 14		92 to 105	98
Week 16		106 to 126	112
Week 20		127 to 154	140
Week 24		155 to 182	168
Week 28		183 to 210	196
Week 32		211 to 238	224
Week 36		239 to 266	252
Week 40		267 to 294	280
Week 44		295 to 322	308
Week 48		323 to 350	336
Week 52		351 to 378	364
Week 56		379 to 406	392
Week 60		407 to 434	420
Week 64		435 to 462	448
Extension #	Ext	≥ 463	476
Follow-up Safety	FU	Follow-up Day	
Follow-up Week 2	FU Week 2	8 to 21	14
Follow-up Week 8	FU Week 8	22 to 70	56
Follow-up Extension #	FU Ext	≥ 71	84

\* OR includes the DBT and OL rimegepant OR analysis periods; on-treatment safety includes the DBT, interim, and OL rimegepant safety analysis periods.

# Denotes an extended visit in the analysis period and is displayed only in listings

Study days are used to define analysis visit windows in all analysis periods except on-rimegepant and follow-up safety. Rimegepant study days are used to define analysis visit windows in the on-DB or OL rimegepant safety analysis period. Follow-up days are used to define analysis visit windows in the follow-up safety analysis period.

Analysis visit windows in the on-DB or OL rimegepant safety analysis period are defined analogously to those in the on-treatment safety analysis period.

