⁸ The electronic subject diary (eDiary) will be dispensed at the Screening Visit, after all Screening Procedures are completed. The subject will be trained on the use of the eDiary. The subject will use the eDiary every day during the Observation Period and Treatment Phase to report migraine occurrence, migraine severity and if the subject treated the migraine.

⁹ Subjects who do not complete the Double-blind, Treatment Phase or do not enter the Open-label, Extension Phase should complete the End of Treatment Visit and 2-Week and 8-Week Follow-up Safety Visits.

¹⁰ While on-study, all visit windows are used for scheduling purposes and all efforts should be made to return subjects to the 28-day schedule if scheduling changes are made at any previous visit(s).

¹¹ The duration between the Pre-Randomization Lab Visit and the Randomization Visit is 4 days. The “+2” days window is included **for scheduling purposes only**. Every effort should be made to collect the Pre-Randomization Lab Visit samples as close to, and within, the 4 days prior to the Randomization Visit as possible. However, for scheduling convenience, this window may be up to 6 days (between the Pre-Randomization Lab Visit and the Randomization Visit).

Table 2. Schedule of Assessments – Open-label Extension Phase Including End of Treatment (EOT)¹⁰ & Follow-up Visits

Procedure	Phone visit to confirm eligibility based on laboratory criteria¹	Week 14 (Day 98 ± 3 days)	Week 16 (Day 112) and 20 (Day 140) (±3 days)	Visits every 4 weeks Week 24 (Day 168) to Week 64 (Day 448) / EOT (±3 days)	2-Week Follow-up Safety Visit (14 days after EOT visit ± 2 days)	8-Week Follow-up Safety Visit (8 weeks (-2 days to +14 days) after EOT visit)
Confirm Week 12 Laboratory Results	X					
Rescue Medication paper diary, Concomitant Medication paper diary and Menstrual Period paper log (female subjects) ²		X	X	X	X ³	X (Concomitant Medication paper diary only) ³
Safety Assessments						
Physical Examinations			X (Week 16 only)	X (Week 24 and 64 / EOT only)		
Vital Signs / Physical Measurements ⁴			X	X	X	
Clinical Safety Laboratory Testing			X (Week 16 only)	X (Week 24, 48, and 64 / EOT only)		
Liver function tests (LFTs)		X	X	X	X	X
Lipid Panel				X (Week 24 and 64 / EOT only)		
ECG			X (Week 16 only)	X (Week 24, 48, and 64 / EOT only)	X	
Urinalysis				X (Week 64 / EOT only)		
Pregnancy Test			X (urine)	X (urine)	X (urine)	X (serum)

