⁵ SAEs, AEs, and Concomitant Procedures must be reported after subject signs informed consent. SAEs should be reported from signing of consent through the 8-week Follow up Safety Visit. Non-serious AEs should be reported from signing of consent through 2-Week Follow up Safety Visit.

⁶ Subjects should finish a bottle of study medication before starting a new bottle. Study drug will be dispensed at monthly (every 4 weeks) study visits, as needed. Unscheduled visits to dispense study medication may be scheduled as needed. Due to the COVID-19 Pandemic, study medication may be shipped to a subject, with up to an 8-week supply. Proper documentation must be maintained in the subject’s source records including shipping vendor, tracking number, confirmation of receipt by subject, and all other relevant information.

⁷ Subjects must take their study medication every other day, regardless of whether or not they have a migraine. During the open-label, extension phase only, if subjects have a migraine on a day that they are not scheduled to take a tablet of study medication, if needed, they may take a study medication tablet to treat a migraine on that calendar day. Therefore, subjects can take a maximum of one (1) tablet of study medication per calendar day. Subjects must report each tablet they take in the eDiary. Doses are not required to be taken in the office on days of a study visit, however dosing requirements and compliance should be discussed with subjects at all visits.

⁸ During the Open-Label, Extension Phase, subjects with 6 or more missed evening reports and 3 or more missed dosing entries per month for 2 months (sequential or non-sequential months) should be considered for discontinuation from the study for poor compliance, after discussion with Sponsor. Month is defined as 4 weeks for the purpose of this protocol.

⁹ The subject will be trained on the use of the eDiary. The subject will use the eDiary every day during the Extension Phase to report migraine occurrence, migraine severity and if the subject treated the migraine.

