4.3.4 End of Treatment (Week 64)

Subjects will return to the study at the end of Week 64 (± 3 days), or at end of treatment for early discontinuations, for review of the electronic diary, assessment of medication compliance, assessment of tolerability and safety (including vital signs, laboratory tests, and electrocardiography) (Table 2). In cases where a Week 64 / End of Treatment (EOT) visit occurs remotely in order to be completed during the protocol required window and due to the COVID-19 Pandemic, the subject should return to the site within the 8 Week Follow-up Safety Visit timeframe (8 weeks from last dose, -2 to +14 days), to complete all procedures that weren't able to be completed remotely. Procedures completed at the Week 64 / EOT Remote Visit do not need to be repeated. Subjects must return the unused study medication and electronic subject diary to the study site. Subjects who do not complete the Double-blind, Treatment Phase and/or

do not enter or complete the Open-label, Extension Phase should complete the End of Treatment Visit, 2-Week Follow up Safety Visit and 8-Week Follow up Safety Visit.

4.3.5 2-Week Follow up Safety Visit

Subjects will return to the study site 14 days after the Week 64/EOT Visit or early discontinuation visit, if applicable, (+/- 2 days) to collect laboratory tests, vital signs, electrocardiography, and assessment of AEs/ SAEs. Subjects will return the prophylactic and rescue medication paper diary and menstrual period (female subjects) paper logs which should be reviewed one final time by study staff. Subjects must continue to track any concomitant medications and therefore must maintain the Concomitant Medication Use Log paper diary through this visit. Investigators should assess subjects for AEs consistent with drug dependency or withdrawal effects and report as appropriate (see Section 7.4).

4.3.6 8-Week Follow up Safety Visit

Subjects will return to the study site 8 weeks after the Week 64/EOT Visit or early discontinuation visit, if applicable (8 weeks (-2 days to +14 days)) to collect liver function tests (LFTs), assessment of SAEs and to have a serum pregnancy test performed (WOCBP). Subjects will return the Concomitant Medication Use Log paper diary for documenting concomitant medications.

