8.2.2 Laboratory Test Abnormalities

The following laboratory test abnormalities should be captured on the non-serious AE CRF page or SAE Report Form (paper or electronic) as appropriate:

1. Any laboratory test result that is clinically significant or meets the definition of an SAE;
2. Any laboratory abnormality that required the subject to have the study drug discontinued or interrupted;
3. Any laboratory abnormality that required the subject to receive specific corrective therapy.

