### **6.7.2 COVID-19 Impact Over Time**

COVID-19 visit impact will be tabulated over time at each analysis visit. The number and percentage of subjects in the categories defined by COVID-19 visit impact type, visit impact characteristics, and visit impact relationship will be presented at each analysis visit in the on-OL rimegepant and follow-up safety analysis periods. If a subject has multiple values (e.g., scheduled missed visit and unscheduled remote visit) in an analysis visit window, then all results will be presented. Percentages are based on subjects with  $\geq 1$  non-missing COVID-19 visit impact in the analysis visit window (see Section 9.1.3).

Missing LFT data impacted by COVID-19 will be tabulated over time at each analysis visit in the on-OL rimegepant and follow-up safety analysis periods as the number and percentage of subjects in the following categories:

1. Missing LFT data, defined as missing values for all of the 4 following LFTs in the analysis visit window: ALT, AST, ALP, and TBL.
2. Missing LFT data at visits impacted by COVID-19, i.e., meeting criteria (1) and having  $\geq 1$  visit impacted by COVID-19 in the analysis visit window (see Section 9.1.3)
3. Missing LFT data at missed visits due to COVID-19, i.e., meeting criteria (1), (2), and having  $\geq 1$  missed visit in the analysis visit window (see Section 9.1.1).

Percentages are based on evaluable subjects at each analysis visit. At an analysis visit in the on-OL rimegepant safety analysis period, evaluable subjects are OL rimegepant treated subjects with (OL rimegepant end date – study drug start date + 1)  $\geq$  lower bound of the analysis visit window. At an analysis visit in the follow-up safety analysis period, evaluable subjects are follow-up subjects with (last contact date – study drug last date + 1)  $\geq$  lower bound of the analysis visit window.

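### SAP Table 4 closes Follow-up Week 8 one or more days before the protocol's 8-week LFT visit window ends, so some compliant late LFTs leave the by-visit summary and can be counted as missing

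*SAP*

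**What the plan says.** **Visit window.** The last follow-up column of protocol Table 2 is headed "8-Week Follow-up Safety Visit (8 weeks (-2 days to +14 days) after EOT visit", and protocol 4.3.6 uses the same anchor. Protocol 4.3.4 and Table 2 footnote 10 cover a subject whose EOT visit was remote. They describe the return within the same visit timeframe as "8 weeks from last dose, -2 to +14 days". The protocol therefore gives one window two anchors.

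**Analysis window.** SAP 7.5 defines the follow-up day as "Measurement date – study drug last date + 1" for measurements on or after the last dose. Table 4 sets Follow-up Week 2 at days 8 to 21 (target 14), Follow-up Week 8 at days 22 to 70 (target 56), and Follow-up Extension from day 71. The footnote on Extension reads "Denotes an extended visit in the analysis period and is displayed only in listings".

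**Missing-LFT table.** The first category in SAP 6.7.2 is "Missing LFT data, defined as missing values for all of the 4 following LFTs in the analysis visit window". In follow-up, the denominator is every follow-up subject whose last contact is on or after the lower bound of the window, which is day 22 for Week 8.

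**AE collection.** Protocol Table 2 footnote 5 says "Non-serious AEs should be reported from signing of consent through 2-Week Follow up Safety Visit", and 8.2.1 agrees. Section 4.3.6 lists LFTs, SAEs and a pregnancy test for the 8-week visit. Section 8.2.2 sends the following to the non-serious AE page or the SAE form, with no end date: "Any laboratory test result that is clinically significant or meets the definition of an SAE".

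**The concern.** The upper bound of 70 looks as if it was meant to match 8 weeks plus 14 days. It does not, because the SAP counts from a different date and adds a day. The visits that fall outside are the late ones, and the upper limit was widened to +14 days so that laboratory draws delayed by COVID-19 would still be in window. A blood sample that complies with the protocol can therefore be missing from the Follow-up Week 8 row. It can also be reported as absent in the one table built to measure LFT data lost during the pandemic.

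The protocol also draws LFTs at 8 weeks after it has stopped collecting new non-serious AEs. It does not say clearly whether an isolated, non-serious LFT abnormality found at that draw is to be recorded.

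**Working it through.** **Inputs.** Protocol 8-week visit: 56 days, -2 to +14, after EOT (Table 2, 4.3.6). Protocol 2-week visit: 14 ± 2 days after EOT (Table 2, 4.3.5). Follow-up day rule and windows: SAP 7.5 and Table 4. L = EOT visit date minus last dose date. L is an assumption, shown from 0 to 21. Values of 0 to 3 are plausible for completers on every-other-day dosing, and longer values are possible after early discontinuation. SAP 7.3 takes the last dose from eDiary dosing data, and SAP 6.2.6.1 generally treats a day with no reported dose as undosed, so unreported final doses lengthen L.

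**The SAP's 70.** 56 + 14 = 70, which is right only if L = 0 and no day is added. The midpoint of targets 56 and 84 is also (56 + 84)/2 = 70. Under the SAP's own day rule the limit is different.

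**Protocol window in SAP follow-up days.**
- Earliest: 56 - 2 + L + 1 = 55 + L.
- Latest: 56 + 14 + L + 1 = 71 + L.
- Permitted days: 71 - 55 + 1 = 17.
- Days beyond 70: (71 + L) - 70 = L + 1, at most 17.

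**2-week visit in SAP follow-up days.** It runs from 12 + L + 1 = 13 + L to 16 + L + 1 = 17 + L. It can reach day 22 once 17 + L ≥ 22, so from L = 5. It always does once 13 + L ≥ 22, so from L = 9.

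| L | 8-week visit, follow-up days | Permitted days outside (of 17) | 2-week visit, follow-up days |
|---|---|---|---|
| 0 | 55–71 | 1 | 13–17 |
| 1 | 56–72 | 2 | 14–18 |
| 2 | 57–73 | 3 | 15–19 |
| 3 | 58–74 | 4 | 16–20 |
| 5 | 60–76 | 6 | 18–22 |
| 7 | 62–78 | 8 | 20–24 |
| 9 | 64–80 | 10 | 22–26 |
| 14 | 69–85 | 15 | 27–31 |
| 16 | 71–87 | 17 | 29–33 |
| 21 | 76–92 | 17 | 34–38 |

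At L = 14 a visit exactly 56 days after EOT is already outside: 56 + 14 + 1 = 71.

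**Last-dose anchor (4.3.4, footnote 10).** The latest day is 56 + 14 + 1 = 71 whatever L is, so the overhang is always one day.

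**What happens to an LFT on day 71 or later.** If no other LFT lies on days 22 to 70, the Week 8 row has no value and SAP 6.7.2 counts the subject as missing. If the 2-week LFT lies on day 22 or later, the subject is not missing, but the 2-week sample becomes the Week 8 value and the 8-week sample appears only in listings.

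**AE passages side by side.** Non-serious AE collection ends at the 2-week visit (footnote 5, 8.2.1), nominally 56 - 14 = 42 days before the 8-week draw. Table 2 still marks its AE/SAE row at the 8-week visit, subject to that footnote. Section 4.3.6 names SAEs only, and 8.2.2 has no end date.

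**The case against.** The strongest reply is that the mismatch is small and costs no liver signal. Much of that stands. At L = 0 the SAP window covers 16 of the 17 permitted days. The follow-up safety period in SAP 7.4 has no upper limit, so late values stay in the follow-up LFT-elevation and worst-abnormality tables, the end-of-follow-up (EOFU) value and the listings. The effect is confined to a by-visit descriptive row and one COVID-19 table.

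Four stronger readings are tempting, and the documents do not support them.

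- A reader might infer that subjects with a long gap before EOT, such as early discontinuers, are the most likely to be counted as missing. From L = 9 the 2-week LFT, if drawn, always falls on day 22 or later. These subjects are then not missing; the risk is that the wrong sample is tabulated.
- A reader might infer that such cases lose their link to COVID-19. The rationale given for the +14 days is a remote contact at 8 weeks with laboratory tests within the next 2 weeks. SAP 7.3 dates the COVID-19 visit by the record, or by the planned date if the visit was missed. At L = 0 a contact at 8 weeks is follow-up day 57, inside the window, and SAP 6.7.2 needs only one impacted visit there.
- A reader might infer that late hepatic events go unrecorded. SAEs, including potential drug-induced liver injury, are collected to the 8-week visit (protocol 8.1.2, 8.1.5).
- A reader might infer harm to the hepatic-AE secondary endpoint. SAP Table 2 defines it on treatment, and the on-treatment safety period ends 7 days after the last dose, so a 2-week cutoff cannot reach it. A general extension of non-serious AE collection would be a design preference, not a correction.

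**Conclusion.** The window error holds. Under the EOT anchor, L + 1 of the 17 permitted days fall outside Follow-up Week 8. Under the last-dose anchor exactly one does. At no value of L does the SAP window cover the whole protocol window. The consequences are an absent Week 8 value, a false missing count in SAP 6.7.2 when no other LFT lies on days 22 to 70, or a 2-week sample shown as Week 8.

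The number of subjects affected cannot be computed, because the documents give neither L nor actual visit dates. For L of 0 to 3, only visits in the last 1 to 4 permitted days are affected. The conclusion on the by-visit row takes LFTs to be among the serum chemistry tests summarized in SAP 6.5.2.3.

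The AE point is limited to an inconsistency: footnote 5, 4.3.6 and 8.2.1 point one way, and the undated rule in 8.2.2 points the other. Both points are worth correcting, and neither changes a formal safety endpoint.

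**What to change.** **SAP Table 4 and 6.7.2.** Assign Follow-up Week 2 and Week 8 by the scheduled follow-up visit, and use the same rule in the missing-LFT table. This removes the overhang and the mislabelled 2-week sample at every L.

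The fallback is to leave Follow-up Week 8 open-ended from day 22 and take the value nearest day 56. This is weaker at long gaps. With both visits on schedule, the 2-week sample is 56 - (15 + L) = 41 - L days from target and the 8-week sample is (57 + L) - 56 = L + 1 days away. These are equal at L = 20, where the SAP tie rule takes the later value, so from L = 21 the 2-week sample is chosen. If the 8-week visit comes on its last permitted day, its distance is L + 15, and the switch comes at L = 14.

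**Protocol window.** Reconcile the EOT anchor (Table 2 header, 4.3.6) with the last-dose anchor (4.3.4, footnote 10).

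**AE recording.** Reconcile Table 2 footnote 5, 4.3.6 and 8.2.1 with 8.2.2, so that sites know whether a non-serious LFT abnormality found at the 8-week draw is recorded.

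**Cost.** The window change is a Table 4 rule and a rerun of the follow-up by-visit LFT rows and the 6.7.2 table. It needs no new data, and SAP version 10.0 was itself issued after final database lock to correct errors. The protocol changes are a few sentences. AE pages not collected for subjects already finished may not be recoverable; if so, state that limitation in the Addendum Report.
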